7.2 Subject Stopping Rules

7.2.1 Stopping challenges

Glucose challenges will be stopped and subject will enter free range glucose control if:

- Subject meets the challenge completion criteria:
 - Hypoglycemia challenge - approximately 120 minutes < 75 mg/dL including 30 minutes < 60 mg/dL
 - Hyperglycemia challenge – approximately 120 minutes > 180 mg/dL including 60 minutes > 325 mg/dL
- Subject requests to end the challenge due to discomfort (desires food and/or insulin)
- Subject ketone measurement ≥ 0.6 mmol/L and glucose is > 300 mg/dL

These subjects will be eligible to continue participating in challenges at future accuracy (sampling) visits. Blood sample collecting and analysis on YSI will continue during this time.

7.2.2 Stopping challenges – no reattempt

Glucose challenges will be stopped and subject will enter free range glucose control if:

- Subject develops significant nausea, vomiting, abdominal pain, chest pain, or develops ketoacidosis
- The subject is unable to cooperate with oral treatment of hypoglycemia
- The glucose is dropping at a rate that may not respond adequately to oral treatment
- The subject experiences symptoms of neuroglycopenia (e.g. lethargy, disorientation, confusion [disordered processing of information or communication], or inappropriate behavior)

Subjects may continue to participate in the study, including future accuracy (sampling) visits but only under observation; participation in future glucose challenges will not be allowed.

7.2.3 Stopping accuracy (sampling) visit

During accuracy (sampling) visits, study procedures other than those required for subject safety will be stopped for that day if any of the following occur:

- The subject had a serious adverse event that is deemed either related to study or in the investigator's opinion requires stopping
- Medical intervention is required to treat severe hypoglycemia (seizure, unconsciousness, etc.)
- Adequate intravenous access cannot be maintained
- The YSI and back-up YSI, (if available), stop functioning and neither can be re-established within 2 hours.
- Subject requests to stop
- Investigator determines it is in Subject's best interest to stop the accuracy (sampling) visit

7.2.4 Subject withdrawal

Subjects will be withdrawn from the study if:

- Subject is noted to be pregnant at any Visit.
- The subject may withdraw if he/she had a serious adverse event that is deemed either related to study device or procedures.

- The subject experiences symptoms of severe hypoglycemia (i.e. hypoglycemic seizure or loss of consciousness)
- Subject experiences DKA (related to the use of the study device) during home use
- Subject voluntarily withdraws from study
- There is an infection at the sensor insertion site that has not responded to treatment within 3 days
- Subject needs an MRI and Sensor is removed and not replaced.
- Investigator determines it is in Subject's best interest to withdraw.
- Subject is lost to follow-up
- Subject dies

7.2.5 Study Exit

A Subject's participation is considered complete after Visit 9 (or Follow-up Visit). A Subject may choose to withdraw at any time without adverse effect on their care. The subject will continue with their medical follow-up, according to standard-of-care. The reason for study withdrawal will be documented.

In the event that a subject withdraws from the investigation and is lost to follow-up, the Investigator will make all reasonable efforts to locate a Subject and encourage Subject to return for Sensor removal. If a subject is lost to follow-up, three separate telephone calls should be made to attempt to schedule a follow-up visit or obtain follow-up information. All attempts and contacts should be documented in the source documents. The subject's Primary Care Physician may also be contacted as stated in the Informed Consent Form. If the Subject does not respond to the three telephone calls, then the Investigator will send a certified letter to the Subject. The Subject will be considered lost to follow-up if this communication is unsuccessful.

7.2.6 Replacement of Subjects

Subjects who exit the study prematurely may not re-enter the study, and will not be replaced.

7.3 Study Stopping Rules

Senseonics may choose to suspend or prematurely terminate the investigation for the following reasons:

- Subject safety issue
- Production limitation

- Administrative decision

The Medical Monitor will review adverse events on a scheduled periodic basis as outlined in Section 13.13. In the case of device-related serious adverse events, the Medical Monitor will consult with the Sponsor and Principal Investigator if appropriate to ensure that the necessary steps are taken to protect the safety and well-being of the Subjects.

The study may be suspended for subject safety reasons. If two or more subjects are stopped (subject withdrawal per section 7.2.4) for the same adverse event related to device, and/or insertion/removal procedure, then the associated portion of the study should be suspended to allow for an investigation. For example, if two subjects are stopped due to infections that do not respond to treatment within three days, new sensor insertions should be suspended while the root cause is investigated.

In the event that that study is stopped, the Investigator will promptly inform the Subjects and ensure appropriate therapy and follow-up, including Sensor removal. Additionally the investigator will promptly inform the IRB and provide a detailed written explanation. The pertinent regulatory authorities will be informed according to local regulations.

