8.2 Potential Risks

The Senseonics CGM System is investigational and is therefore not considered to be a medical standard. To evaluate the Senseonics CGM system, blood draws for glucose measurements will be performed more frequently than in daily routine. In addition to use of the System, hyperglycemia and hypoglycemia challenges may be performed exclusively for study purposes.

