8.2.3 Risks Associated with Participation in the Clinical Investigation

This clinical investigation involves subjects with diabetes mellitus. These subjects may experience hyperglycemia and hypoglycemia as a consequence of their existing condition and medical management (e.g. insulin administration). For this study, hyperglycemia and hypoglycemia will not be reported as adverse events unless meeting criteria of a Serious Adverse Event. Episodes of hyperglycemia and hypoglycemia as documented by the Subject SMBG Meter will be reported in an extra listing separate from the AE listings. Should a known side effect(s) occur to administered medication(s) used in the intervention, such effects will be reported as part of the adverse event description and will not be considered a separate adverse event.

The amount of blood drawn for in-clinic testing during the study is below the acceptable limits of blood donation of approximately 475 mL; hence it does not pose any additional unacceptable risk to the subjects.

This clinical investigation involves the following procedures that present risk: placement of an intravenous catheter, frequent blood sampling, and conduct of hyperglycemia and hypoglycemia challenges at the clinic visits. In addition, Subjects in this study may use an insulin pump or syringes to administer subcutaneous insulin.

The following risks are potentially associated with such procedures:

- Routine administration of insulin may cause hematoma, redness, swelling and itch at the injection site, skin rash, itch, sweating, gastro-intestinal complaints, edema, difficulty breathing, palpitations and drop in blood pressure, and even death.
- Hypoglycemic symptoms requiring medical intervention which may include seizures, neuroglycopenia, coma and even death (including occurrence during home use)
- Insulin administration leading to hypoglycemia include: cold sweating, cool and pale skin, fatigue, nervousness, shakiness, anxiety, weakness, confusion, feeling of numbness, hunger, impairment of vision, problems with concentration, headache, nausea, palpitations, coma, or death.

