Causality: The causal relationship should be determined with respect to the investigational device, the insertion or removal procedure, or other study-related procedures.

None: The event is not associated with the device or procedure. There is no relation between the event and the device or procedure.

Possibly Related: The temporal sequence between the device or procedure and the event is such that the relationship is not unlikely or there is no contradicting evidence that can reasonably explain the Subject's condition. There is a possibility of any relation between the event and the device or procedure.

Related: The temporal sequence is relevant or the event abates upon device application completion/removal or the event cannot be reasonably explained by the patient's condition or comorbidities. The event is related or most likely associated with the device or procedure.

Unknown: There is no evidence or relevant data available to assess the relationship between the event and the device or procedure.

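### The only counted pause rule in Protocol 7.3 leaves out harm caused by the glucose challenges, so a pause after repeated challenge seizures would rest on discretion

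*Protocol*

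**What the plan says.** The counted rule is in Protocol 7.3. Its trigger reads "If two or more subjects are stopped (subject withdrawal per section 7.2.4"), and it continues "for the same adverse event related to device, and/or insertion/removal procedure, then the associated portion of the study should be suspended" so that the cause can be investigated. The section's example is two subjects stopped for infections that do not respond to treatment.

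The causality scheme in Protocol 9.1 is wider: "The causal relationship should be determined with respect to the investigational device, the insertion or removal procedure, or other study-related procedures".

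On the challenges, Protocol 8.2 says that "hyperglycemia and hypoglycemia challenges may be performed exclusively for study purposes". Protocol 8.2.3 lists among the risks of participation "Hypoglycemic symptoms requiring medical intervention which may include seizures, neuroglycopenia, coma and even death".

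The mandatory withdrawal criteria in 7.2.4 include: "The subject experiences symptoms of severe hypoglycemia (i.e. hypoglycemic seizure or loss of consciousness"). For serious adverse events (SAEs) in general, the same list is permissive: "The subject may withdraw if he/she had a serious adverse event that is deemed either related to study device or procedures".

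Section 7.3 also contains discretion. The sponsor may suspend or terminate for a subject safety issue, with no limit on cause or count. The Medical Monitor consults with the sponsor and principal investigator, where appropriate, on device-related SAEs. Section 13.13 makes the monitor responsible for seeing the stopping rules implemented but adds no threshold. Protocol 11.1.8 and SAP 6.6 give the interim analysis no stopping rule.

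**The concern.** The protocol asks investigators to assign one of three kinds of cause and then builds its counted pause rule on two of them. The omitted kind covers the challenges, which deliberately drive glucose low or high for study purposes. Section 8.1 offers subjects no direct benefit.

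The other subjects are the ones exposed. Challenges run from Visit 3 (Day 1) to Visit 8 (Day 90), and enrollment is staggered over about two months. When a second subject is harmed, many challenges may still lie ahead. For device and insertion/removal harm the protocol fixes in advance when to pause and investigate. For challenge harm it does not, and it gives no reason for the difference.

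**Working it through.** **No figure to reproduce.** The count of two has no derivation or stated operating characteristics. The check is to read the rule against sections 7.2.4 and 9.1.

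**Both halves of the rule, by scenario**

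| Two subjects with the same event | Withdrawn under 7.2.4? | Cause counted in 7.3? | Rule met? |
|---|---|---|---|
| Infection at the sensor site, unresponsive to treatment | Yes, required | Yes | Yes |
| Seizure attributed only to a hypoglycemia challenge | Yes, required | No | No |
| Device-related SAE, both subjects stay | No, optional | Yes | No |
| Injury at planned removal, both subjects complete | No | Yes | No |

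The second row is the main point: only the cause wording stops the rule from being met. The last two rows are a separate, secondary matter. They fail because the rule counts withdrawals, not events. A subject injured at planned removal normally goes on to follow-up, where "A Subject's participation is considered complete after Visit 9 (or Follow-up Visit").

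**Exposure (upper bound: all 36 subjects eligible, no attrition)**

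- Visits 3, 4 and 5 have one hyperglycemia and one hypoglycemia challenge each: 3 × 2 = 6 per subject.
- Visits 6, 7 and 8 have one challenge each, of a type set by the first glucose value (5.12.3): 3 per subject.
- Total: 36 × (6 + 3) = 324.
- Hypoglycemia challenges: from 36 × 3 = 108, if every later challenge is hyperglycemic, to 36 × 6 = 216, if every later one is hypoglycemic.

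Real numbers will be lower. Section 5.12.1 excludes subjects with gastroparesis from challenges and does not expect subjects who are not on insulin to have hypoglycemia challenges.

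**Illustration only.** The documents give no event rate. Assume a common per-subject risk p, independent between subjects. Then

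P(two or more of 36) = 1 − (1−p)^36 − 36·p·(1−p)^35.

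- p = 1%: 0.050
- p = 2%: 0.162
- p = 3%: 0.294
- p = 5%: 0.543

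For events attributed only to a challenge, the present rule fires with probability 0 at every p. With the cause wording extended, it would fire with the probabilities listed, because withdrawal after such a seizure is mandatory.

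**Secondary point, same formula.** For a device-related SAE with p = 5%, two or more subjects are affected with probability 0.543. If only a share w of affected subjects withdraws, p is replaced by p × w. The withdrawal count then fires with probability 0.227 at w = one half, 0.074 at w = one quarter, and 0 if none withdraws. Both p and w are assumptions.

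**The case against.** The strongest reply is that the counted rule is only one safeguard among several. A reader might infer that repeated challenge seizures would not pause the study. The documents do not support that. Section 7.3 permits suspension for subject safety whatever the cause or count. Section 9.3 brings every SAE to the sponsor within 48 hours, with causality recorded for other study procedures. Section 8.3 has an independent monitor review SAEs without a device limit, and 13.13 has the monitor evaluate all device- or procedure-related events under a Safety Management Plan that is not among the documents reviewed. Individual stops exist in 7.1.4.1 and 7.2.2 to 7.2.4, and a clinician is present or available during challenges. All of this stands. None of it supplies a count at study level, and the individual stops do not add up to one.

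A seizure judged related to the device would count. One judged only possibly related might: section 11.2 treats that grade as related for analysis, but 7.3 does not say whether it does the same.

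A reader might also infer that SAEs in continuing subjects, or removal injuries, can never trigger the rule. That goes too far. Voluntary withdrawal, or withdrawal in the subject's best interest, is open under 7.2.4, and some removals happen early, for example for infection (7.1.2). Planned removals come around Day 90. With about two months of enrollment and insertion within 30 days of screening, insertions should be nearly over by then, so little but removal itself would be left to pause. Suspending removal would conflict with 4.7, which wants sensors out before Day 101, and with 7.3, which requires removal if the study stops.

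**Conclusion.** The gap in cause is real and follows from the text alone. The counted rule omits one of the protocol's own causal categories, so two mandatory withdrawals for challenge-induced seizure or loss of consciousness would not trigger it. A pause would rest on sponsor discretion and Medical Monitor review.

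This assumes that the events are attributed to the challenge and not to the device, and that they are recorded as adverse events. Under 8.2.3 the latter requires a hypoglycemic event to meet the SAE criteria.

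The range of 0.050 to 0.543 for p between 1% and 5% shows only what the assumed risks imply. It is not evidence that such events are likely, and the conclusion does not depend on it. No endpoint or analysis is affected. This is a recommended correction to subject protection, not a defect that invalidates the plan.

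Counting withdrawals instead of events is a secondary matter for the sponsor to consider.

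**What to change.** Reconcile 7.3 with 7.2.4 and 9.1:

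- **Cause.** In the counted rule, extend the causes to *related to the device, the insertion/removal procedure, or another study-related procedure (including glucose challenges)*. Keep the count of two and the limit to the associated portion of the study, so that the portion suspended would be the challenges.
- **Consultation.** Extend the Medical Monitor sentence in 7.3 from device-related to any study-related SAE.
- **For consideration, not required.** Decide whether repeated related SAEs or removal injuries should count when the subject stays or completes. Any such change must not suspend sensor removal itself.

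The first two changes are wording only. They set no glucose threshold, dose or treatment rule, and they use causality data that 9.3 already collects. The cost is that the challenges may be paused for investigation somewhat more often.

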7.4 Termination of Investigator or Investigational Site

Senseonics reserves the right to terminate an investigator/investigational site for any of the following reasons, which are considered major deviations:

- Failure to secure subject informed consent including protection of personal data prior to enrollment
- Failure to report unanticipated adverse device effects and serious adverse events to Senseonics and to the IRB/ EC within its required reporting time after learning of the event
- Repeated investigational plan deviations
- Loss of or unaccounted for investigational product inventory.

8 RISK AND BENEFIT ANALYSIS

8.1 Potential Benefits

There will be no direct benefit to the subjects participating in the investigation other than the knowledge that they are contributing to the overall advancement of medical and scientific knowledge that may benefit future subjects with similar conditions. The CGM data collected will not be used for any clinical decisions or care.

8.2 Potential Risks

The Senseonics CGM System is investigational and is therefore not considered to be a medical standard. To evaluate the Senseonics CGM system, blood draws for glucose measurements will be performed more frequently than in daily routine. In addition to use of the System, hyperglycemia and hypoglycemia challenges may be performed exclusively for study purposes.

8.2.1 Anticipated Adverse Effects

The following adverse effects could occur in association with insertion, removal, and/or use of the Senseonics CGM System Sensor and/or Transmitter:

- Infection, local or systemic, possibly resulting in sensor removal
- Excessive bleeding during insertion or removal
- Bruising or swelling
- Poor wound healing after insertion or removal
- Keloid and/or scar formation
- Excessive or prolonged pain or discomfort at the Sensor site
- Nerve damage causing tingling, numbness, pain or weakness
- Uncomfortable heating
- Burn
- Electrostatic shock
- Skin irritation and/or redness
- Itch
- Discoloration of skin
- Hematoma formation
- Device migration
- Skin erosion
- Allergic reaction to the device components, local anesthetic, or other medication or materials used in the procedure
- Anxiety and/or nervousness and/or lack of sleep
- Device fragments or particulate matter remaining in the body
- Failure to retrieve device or device left behind
- Difficulty in removing device that may require surgery
- Device malfunctions of the Sensor and/or Transmitter with possible need to remove and/or replace the Sensor and/or Transmitter
- Burning sensation or pain.
- Elevated blood pressure
- Water retention in the tissue, swelling or edema
- Airway spasms

- Shortness of breath
- Circulatory disorders
- Confusion
- Disorientation
- Increased or decreased sensitivity to touch or pain
- Metallic taste
- Sleepiness
- Visual disturbances and/or blurred vision
- Tinnitus
- It is possible that the local anesthetic could cause a reaction other than listed or previously seen.
- Fluid/electrolyte disturbances such as fluid retention
- Muscle weakness
- Osteoporosis
- Peptic ulcer
- Pancreatitis
- Ulcerative esophagitis
- Impaired wound healing
- Headache
- Psychic disturbances and mood swings
- Convulsions
- Glaucoma
- Weight gain
- Nausea and/or vomiting
- Malaise
- Irritability
- Insomnia
- Heartburn
- Hyperglycemia
- Ketosis
- Headaches
- Dizziness, lightheadedness, and/or fainting
- It is possible that the use of the Senseonics CGM system could cause a reaction other than listed or previously seen.
- It has not been determined whether the risks usually associated with injectable dexamethasone apply to the use of dexamethasone elution ring, a highly localized, controlled-release device.
- The dexamethasone ring could cause other adverse events not listed or previously seen.

- Other adverse events typically related to diabetes treatment and diabetes are unknown

8.2.2 Residual Risks Associated with the Investigational Device

Components of the Senseonics CGM System are manufactured under the Quality System provisions of ISO 13485:2003.

Risk analysis has been performed and adequate control put in place as prescribed in relevant provisions of IEC 62304, ISO 14971, and IEC 60601-1, in accordance with the requirements of ISO 13485:2003. Residual risks associated with the device included risks in the categories of electromagnetic and thermal energy, biocompatibility, biologic, chemical and mechanical factors, and user-related error. All identified risks have been reduced as far as possible using various control methods including software revision and re-validation, hardware design modification, packaging and sterilization process validation and labeling revision. The calculated residual risks were determined to be acceptable for conduct of this clinical investigation.

8.2.3 Risks Associated with Participation in the Clinical Investigation

This clinical investigation involves subjects with diabetes mellitus. These subjects may experience hyperglycemia and hypoglycemia as a consequence of their existing condition and medical management (e.g. insulin administration). For this study, hyperglycemia and hypoglycemia will not be reported as adverse events unless meeting criteria of a Serious Adverse Event. Episodes of hyperglycemia and hypoglycemia as documented by the Subject SMBG Meter will be reported in an extra listing separate from the AE listings. Should a known side effect(s) occur to administered medication(s) used in the intervention, such effects will be reported as part of the adverse event description and will not be considered a separate adverse event.

The amount of blood drawn for in-clinic testing during the study is below the acceptable limits of blood donation of approximately 475 mL; hence it does not pose any additional unacceptable risk to the subjects.

This clinical investigation involves the following procedures that present risk: placement of an intravenous catheter, frequent blood sampling, and conduct of hyperglycemia and hypoglycemia challenges at the clinic visits. In addition, Subjects in this study may use an insulin pump or syringes to administer subcutaneous insulin.

The following risks are potentially associated with such procedures:

- Routine administration of insulin may cause hematoma, redness, swelling and itch at the injection site, skin rash, itch, sweating, gastro-intestinal complaints, edema, difficulty breathing, palpitations and drop in blood pressure, and even death.
- Hypoglycemic symptoms requiring medical intervention which may include seizures, neuroglycopenia, coma and even death (including occurrence during home use)
- Insulin administration leading to hypoglycemia include: cold sweating, cool and pale skin, fatigue, nervousness, shakiness, anxiety, weakness, confusion, feeling of numbness, hunger, impairment of vision, problems with concentration, headache, nausea, palpitations, coma, or death.
- Hyperglycemia and diabetic ketoacidosis requiring medical intervention which may include potential complications such as nausea, vomiting, abdominal pain, dehydration, difficulties with breathing, confusion, bad breath, low blood pressure, coma, kidney failure, cardiac arrhythmia, myocardial infarction, cerebral edema, rhabdomyolysis and even death (including occurrence during home use).
- Excessive pain during insertion of the IV catheter
- Multiple sticks due to IV placement
- IV placement failure
- Restricted mobility
- Fainting, dizziness, lightheadedness or low blood pressure in response to blood sampling
- Bleeding during catheter insertion or infusion pump infusion set change
- Bruise formation at catheter site or due to infusion pump use
- Fluid overload due to saline flushes of IV catheter
- Skin redness or scarring due to infusion pump use
- Temporary muscle or nerve irritability, arrhythmia or death due to electrolyte disturbance
- Tissue damage (burn) due to heating devices
- Severe gastro-intestinal distress
- Difficulty breathing
- Cardiovascular symptoms
- Nerve damage
- Rash
- Pain
- Infection, local or systemic
- Blood clots, which may cause inflammation, swelling and pain
- Circulatory disorders, including but not limited to low blood pressure
- Skin irritation or pruritus due to medical adhesive (electrodes, tapes, etc.)
- Infection, inflammation or phlebitis at IV insertion sites or infusion pump infusion set sites
- Edema at the insertion site

- Erythema at the insertion site
- Allergic reaction
- Excessive pain or burning sensation associated with injections
- Headache
- Vasovagal response or fainting
- Anemia due to blood sampling
- Muscle soreness or extremity injury from exercise including weight lifting

Subject may have an X-ray or ultrasound of the sensor site. X-rays may cause damage to cells in the body, which in turn may increase the risk of developing cancer. This increase in risk associated with each X-ray procedure is extremely low but does slowly increase with the increasing number of X-rays tests you have.

Even though there are no known risks of ultrasound imaging, it can produce effects on the body. When ultrasound enters the body, it heats the tissues slightly. In some cases, it can also produce small pockets of gas in body fluids or tissues (cavitation). The long-term effects of tissue heating and cavitation are not known.

